Intervention(s)/Procedure(s)	
Prior to arrival, participants will be instructed to consume fluids and to come to the test site with a full bladder. Upon arrival at the test site, participants will be consented and screened against inclusion/exclusion criteria. Those meeting eligibility criteria will be assigned a treatment order. Participants will be divided into two cohorts.
 
Cohort A: Non morbidly obese men: BMI <40
 
Cohort B: Morbidly obese men: BMI ≥40
 
Participants will be placed in the test area, instructed to undress, and put on a gown. The Health Care Professional (HCP) will complete a visual assessment of the participant's pubic/ genital region to ensure that the participant is trimmed and assess the anatomy. Trimmers can be provided if the participant did not arrive to the site trimmed. The HCP will then assess for a buried penis and/or anatomical compatibility with traditional sheath style condom catheters for each participant. "A buried penis refers to a normal-sized phallus encompassed by either skin, subcutaneous tissue, and/or fat in the prepubic area" causing a reduced visible and/or functional length of the phallus.¹¹
 
Void 1:
 
The bed in the test area will be set with a pre-weighed absorbent pad and a pre-weighed urine collection canister (with the lid). Once the participant feels the need to void, the Health Care Professional (HCP) will place either the PureWick™ MEC (Device A) or the Sage PrimoFit™ (Device B) (depending on randomized treatment order) according to the device instructions for use (IFU) and confirm the correct placement prior to the voiding episode. The participant will be placed in a semi-fowler position (head of bed elevated approximately 30 degrees) in a hospital bed and turned to one side using a turning wedge prior to the voiding episode. Participants will be monitored for approximately 2 hours from the time of the device application, through one void. (The skin needs to be assessed at least every two hours while wearing a MEC.) After the void, the pre-weighed absorbent pad and urine collection canister will be weighed (with the lid), and weights documented in the source. The Pure Wick MEC or Sage PrimoFit™ will be removed by the HCP. After removal, the HCP will note any signs of irritation/injury in the perineal area. Any unresolved erythema (redness), erythema (swelling), bleeding, injury, or rash should be recorded as an Adverse Event.

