4.2 Scientific Rationale for Study Design

This study will assess the performance of and user experience with PureWick™ Male External Catheter when compared with a marketed comparator, Sage PrimoFit™ Male External Catheter. To best mimic potential users of the study devices, male participants ≥ 18 years of age will be enrolled. Additionally, enrollment will target approximately 50% of the sample size of men in two different BMI cohorts so that potential differences based on anatomy can be characterized. As such, participants in this study adequately represent the patients who would use the device in the hospital setting.

In the critical care setting or with patients that have limited mobility, it is commonly ordered for patients to be repositioned and turned on their side every two hours. A turning wedge is a device used by hospitals to prop the patient onto their side. Additionally, the patient is commonly ordered to elevate the head of the bed. The Primary endpoint provides a reliable and valid measurement of the efficacy related to the function of the device by capturing and weighing all urine output per void, including leakage, and dividing by the captured amount of urine in the canister. A higher captured rate constitutes a more meaningful effect. Questionnaires using a 5-point Likert scale will be administered to each participant to assess comfort, and to each HCP to assess ease of use. A higher Likert score, such as a 4 or 5, constitutes a more meaningful effect on these

secondary endpoints. Furthermore, this study seeks to understand if the PureWick™ MEC will perform effectively in male anatomy that is not compatible with traditional sheath-style condom catheters in a controlled setting.

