7.5 Test Procedure

1. After enrollment and randomization, the participant will be brought to the testing area and instructed to undress and put on a gown.
 - a. The bed in the test area will be set with clean sheets, a pre-weighed absorbent pad and a pre-weighed urine collection canister.
2. The Health Care Professional (HCP) will complete a visual assessment of the participant's pubic and genital region to ensure that the participant is trimmed and assess the anatomy.
 - a. Unless the participant arrives with their pubic hair pre-trimmed, the participant's pubic hair will be clipped by themselves or a trained professional.
 - b. The HCP will then complete a brief survey to assess for a buried penis and/or anatomical compatibility with traditional sheath style condom catheters for each participant. "A buried penis refers to a normal-sized phallus encompassed by either skin, subcutaneous tissue, and/or fat in the prepubic area" causing a reduced visible and/or functional length of the phallus.¹¹ for each participant.
3. The HCP will place either the PureWick™ MEC or the Sage PrimoFit™ device (depending on randomized sequence) according to the device IFU and confirm the correct placement.
4. The participant will be placed in a semi-fowler position in the hospital bed and turned to one side using a turning wedge. The HCP should reconfirm correct device placement after repositioning.
5. The HCP will ensure the collection cannister and suction tubing are connected to wall suction and the suction is set to a minimum of 40mmHg continuous suction.
6. Once setup is confirmed and the device is placed, the participant will be allowed to spontaneously void. The participant will be monitored for up to 2 hours, through one void.
7. After the void, the pre-weighed absorbent pad and urine collection canister (with lid) will be weighed and the weights will be documented in the source documents.
8. The Pure Wick MEC or Sage PrimoFit™ will be removed by the HCP according to the IFU and discarded.
9. After removal, the HCP will note any signs of irritation/injury in the perineal area.
 - a. Any unresolved erythema (redness), erythema (swelling), bleeding, injury or rash must be recorded as an Adverse Event.

10. The HCP will complete a brief survey to assess device ease of use for the participant just treated.
11. Participant will be asked not to void and to drink approximately 16 ounces of liquid.

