10.5 Primary Endpoint(s)

Capture rate is defined by:

$$\text{Captured urine weight} / (\text{captured urine weight} + \text{leaked urine weight})$$

The primary endpoint will be evaluated against the following hypotheses:

H₀: Capture rate of PureWick™ Male (system) = Capture rate of established comparator (Stryker/ Sage PrimoFit™)

H₁: Capture rate of PureWick™ Male (system) ≠ Capture rate of established comparator (Stryker/ Sage PrimoFit™)

A two-sided paired t-test will be used to test the hypotheses and p-value will be derived. A p-value < 0.05 , combined with a capture rate in favor of PureWick™, indicates that PureWick™ is superior to PrimoFit™ in terms of urine capture.

An exploratory analysis will be performed using regression, where subject may be included as the random effect, and period, sequence, treatment may be included as fixed effects.

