## 2.7 Endpoints

### 2.7.1 Primary Endpoints

Primary endpoint is capture rate following void (captured as % of urine captured by device and collected in canister, measured by weight), PureWick™ Male (System) compared with Stryker/ Sage PrimoFit™.

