## 5 Statistical Analysis/Calculations

### 5.1 Derived Variables

- Subject who are deemed unable to used traditional sheath style condom catheters:  
Answered “No” to “Is the participant’s anatomy compatible with traditional sheath-style condom catheters?” on Case Report Form (CRF) page entitled Professional Anatomical Compatibility.
- Capture rate:  
Captured urine weight / (captured urine weight + leaked urine weight), where
  - Captured urine weight is defined as canister final weight (g) - canister starting weight (g), and
  - Leaked urine weight is defined as pad final weight (g) - pad starting weight (g).
 A void of which (captured urine weight + leaked urine weight) < 10 g is considered not evaluable for the purpose of analyzing primary endpoint and secondary endpoint with hypothesis-testing.

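### Urine that leaks onto the gown or sheets is never weighed, so it drops out of the capture-rate denominator, although protocol 4.2 says all output is counted

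*Protocol*

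**What the plan says.** Protocol 4.2 calls the primary endpoint reliable and valid because it rests on "capturing and weighing all urine output per void, including leakage, and dividing by the captured amount of urine in the canister".

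The procedure is narrower. Protocol 7.5, step 1a: "The bed in the test area will be set with clean sheets, a pre-weighed absorbent pad and a pre-weighed urine collection canister". The sheets are clean but have no starting weight. Step 1 puts the participant in a gown, also without one. Step 4 has him semi-fowler and turned to one side on a wedge. Step 7 then says "After the void, the pre-weighed absorbent pad and urine collection canister (with lid) will be weighed". The Synopsis (1.1) agrees ("After the void, the pre-weighed absorbent pad and urine collection canister will be weighed (with the lid), and weights documented in the source"), and 4.1 repeats it.

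Protocol 10.5 puts captured plus leaked weight in the denominator without saying how leakage is measured. SAP 5.1 supplies the rule ("Leaked urine weight is defined as pad final weight (g) - pad starting weight (g"), with captured urine as canister gain. The evaluability floor uses the same two gains: "A void of which (captured urine weight + leaked urine weight) < 10 g is considered not evaluable". No section weighs the gown or sheets, records wetting off the pad, or says how to handle it.

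**The concern.** Leakage is the quantity that separates two devices on capture rate. Participants void on their side, and the enrolment target puts half of them at BMI 40 or above, so some urine may run past the pad. Under SAP 5.1 it is treated as if it had never been voided. A void whose whole leak landed on the gown would score 100%.

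Within a void the error has one sign: it can raise the rate but not lower it. What matters for the test is whether it survives in the paired difference, and the trial would hold no data to answer that. Protocol 11.3 notes that missing observations cannot be recovered from another source, so any check has to be planned in advance.

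**Working it through.** **The plan's own figure.** Protocol 10.2 and SAP 2.4: n = 44, two-sided paired t-test at 0.05, difference of half an SD, 90% power. Noncentral t with df = 43 and noncentrality 0.5 × √44 = 3.317 gives 0.900. It reproduces, so the sample size is not in question.

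**Error in one void.** Let C = canister gain, L = pad gain, U = off-pad urine, T = C + L + U, and m = C/(C + L) the measured rate. Then

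m − C/T = m × U/T,

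which is zero when U = 0 and otherwise cannot be negative.

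**Effect on the paired difference.** From the documents: n = 44 and the example SD of 10 points. Assumed: all leak sizes, off-pad amounts, capture rates and void weights. (125 g corresponds roughly to the 125 mL scan threshold before void 2.)

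1. *Equal grams lost.* Full-total rates 95% and 90%, U = 5 g on both devices. The measured difference is 5.0 × T/(T − 5): 5.0 × 250/245 = 5.1 points at 250 g, and 5.0 × 125/120 = 5.2 at 125 g. Nearly unaffected.

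2. *Equal share f of each leak lost.* With leak fraction l, the measured rate is (1 − l)/[(1 − l) + l(1 − f)]. Leaks of 5% and 10%, true difference 5.0 points:
   - f = 25%: 0.95/0.9875 − 0.90/0.975 = 0.9620 − 0.9231 = 3.9 points. Power about 71% with SD held at 10.
   - f = 50%: 0.95/0.975 − 0.90/0.95 = 0.9744 − 0.9474 = 2.7 points. Power about 42% with SD held at 10.

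   Holding the SD at 10 is the severe case. If the SD shrank in the same proportion as the difference, their ratio would stay at 0.5 and power at about 90%. The reported difference would still be too small.

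3. *Loss differs by device.* A 5 g excess on one device at m = 90%: 0.90 × 5/T = 1.8 points at T = 250 g, 3.6 at 125 g, 1.1 at 400 g. The sign depends on which device loses more.

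**The 10 g floor.** A 125 g void falls below it only if more than 125 − 10 = 115 g misses both canister and pad. This is a minor point.

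**The case against.** The strongest reply is that off-pad loss may be nil. Pad size and placement are not stated, and a pad that catches every leak removes the error. Each man is also his own control, and the simplest assumption, a similar share of every leak missing the pad, pulls the difference towards zero and so does not favour a false superiority claim. All of this stands. It limits what can be claimed about size, but it does not reconcile 4.2 with SAP 5.1.

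Two stronger readings are tempting. A reader might infer that the comparison is biased towards PureWick. The documents do not support that: nothing suggests that one device leaks off the pad more than the other, and the direction is open. A reader might also infer that urine held in the device, or released at removal, has no defined status. The endpoint label is loose ("captured as % of urine captured by device and collected in canister, measured by weight"), but SAP 5.1 is operational and step 7 weighs before step 8 removes the device, so that urine counts as neither captured nor leaked.

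A practical objection also has force. Weighing only items that look wet would hand the primary endpoint to the judgement of an HCP who is not blinded to device (6.5.2). Any added weighing should therefore be unconditional.

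**Conclusion.** The mismatch holds on the text alone: 4.2 claims that all output is weighed, while the procedure and SAP 5.1 count canister and pad only. Any urine on the gown or sheets inflates that void's rate. Bias in the device comparison is possible but not shown. It ranges from none (no off-pad loss), through near-cancellation (equal grams) and shrinkage from 5.0 to 3.9 or 2.7 points (equal shares), to a shift of about 1 to 4 points either way (5 g excess on one device, voids of 400 g down to 125 g). Every one of these amounts is an assumption. The firm conclusion is that the trial as planned could not show which case applied, and a cheap prospective record would.

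**What to change.** 1. **Protocol 1.1, 4.1 and 7.5.** Use a fresh pre-weighed gown and draw sheet for each void. Re-weigh both with the pad after every void, whether or not they look wet, at one stated point in the sequence that is the same for both devices. Record off-pad wetting yes/no for every void.
2. **SAP 5.1.** Define leaked urine as the summed gain of pad, gown and draw sheet, apply the 10 g floor to the new total, and report the pad-only rate as a sensitivity analysis.
3. **Protocol 4.2.** Its ratio is worded upside down, with total output divided by captured urine. Align it with 10.5: captured over captured plus leaked. Add one sentence saying that urine held in the device or released at removal counts as neither. If the gown and sheet are collected after removal, that sentence must allow for spillage onto them.

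If weighing these items is judged impractical, keep the pad-only rate as primary, record off-pad wetting yes/no by device, prespecify a sensitivity analysis of the affected voids, and narrow 4.2 to say that only canister and pad urine is weighed.

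**Cost.** Two more items weighed per void, one CRF field, some handling of linen around the participant, some added weighing noise (including moisture that is not urine), and possibly slightly lower reported capture rates. Scales are already listed in 6.3, and the sample size does not change.

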2.3.1 Risk Assessment

Potential Risk of Clinical Significance	Summary of Data/Rationale for Risk	Mitigation Strategy
Study Intervention: PureWick™ Male External Catheter		
Potential adverse events: 
 • Skin injury • Skin irritation • Allergic reaction 	PureWick™ MEC is an external device placed around the base of the penis and adhered to the pelvic skin.	
 • To avoid potential skin injury, never pull the device directly away from the patient. Always peel in the direction from head to foot. • Perform perineal care using the included wipes and assess skin integrity before device application. • Assess the device placement and patient's skin at least every 2 hours. • Monitor for pulling and tension on the device after turning the patient. • Replace the device every 24 hours or if soiled with feces, blood, or semen. • Remove the device prior to ambulation.
Study Intervention: Sage PrimoFit™		
Potential adverse events: 
 • Skin injury • Skin irritation 	Sage PrimoFit™ is an external urine management device for the male anatomy that adheres to the pelvic and abdominal skin.	
 • Clean, prep, and dry patient's genital area before device application • Perform skin assessment every 2 hours

Potential Risk of Clinical Significance	Summary of Data/Rationale for Risk	Mitigation Strategy
		
 Assess device periodically to ensure proper placement, particularly after turning or repositioning patient. Device can be left on skin for up to 24 hours. Replace device if soiled with stool or bodily fluids other than urine. Discontinue use during patient ambulation.
Study Procedures		
Discomfort due to full bladder	Participants will be asked to refrain from voiding until bladder volume reaches $\geq 125\text{mL}$ to ensure a full second void.	
 Participants who meet the eligibility criteria and follow study instructions should not have a bladder that is uncomfortably full.

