5.2 Exclusion Criteria

Participants are excluded from the study if any of the following criteria apply:

1. Urinary incontinence which does not allow the subject to spontaneously void
2. Frequent episodes of bowel incontinence
3. Has Urinary Retention
4. Has any irritation, wound, open lesion, at the application site, on the genitalia, perineum, or sacrum
5. Recent surgery of the external urogenital tract, penis, or pubic area
6. Not able to comply with study procedures independently without required assistance
7. Any other condition that, in the opinion of the investigator, would preclude them from participating in the study

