16.2 Appendix 2: Sage PrimoFit™ Instructions for Use (IFU)

Sage

PrimoFit™

External Urine Management
for the Male Anatomy

stryker

Male
[anatomy]

Contents: (1) PrimoFit, adult size **Reorder #5404**

- Single use only.
- Not made with natural rubber latex.
- Non-sterile.

Indications

For the non-invasive external collection of urine for adult patients with male anatomy who require urine management.

Contraindications

- Do not use on patients with urinary retention.

Cautions

- Not intended for use on patients in the prone position.
- Not intended for use on patients with female anatomy.
- Not intended for use for stool collection.
- Use caution if using on patients with altered mental status.

Supplies needed

- Suction canister
- Suction tubing

Directions

Prior to use

- Perform skin assessment every 2 hours per hospital protocol.
- Refer to manufacturer's instructions for suction set up.
- Ensure patient meets hospital protocol prior to placing device. If necessary, clip patient hair per hospital protocol.

Placement

- Step 1** Set up suction canister and tubing according to hospital protocol. Replace tubing and empty and/or replace suction canister per hospital protocol.
- Step 2** Place patient in supine position and separate patient's legs.
- Step 3** Clean, prep and dry patient's genital area according to hospital protocol. If necessary, clip patient hair per hospital protocol.
- Step 4** Remove device from packaging.
- Step 5** Remove the base adhesive liner. (Figure 1)
- Step 6** Position the device with adhesive side toward the patient, with the tabs facing upward and the opening of the base adhesive in line with the patient's penis.
- Step 7** Holding the tabs, position the base adhesive up and around the patient's penis against the skin. To ensure adequate adhesion, apply pressure all the way around the base adhesive against the skin. (Figure 2)
- Step 8** Position the patient's penis into the chamber. (Figure 3)
- Step 9** Remove the adhesive pad liner (Figure 4). Pull the device up until fully extended over the patient's penis and suprapubic region and adhere the adhesive pad onto the patient's abdomen. (Figure 5)

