- Step 10** Ensure adequate length of suction tubing is available. Attach suction tubing to the device at the suction tubing adapter. Ensure connection of suction tubing to device is secure and connected at all times while device is in use. Confirm there are no kinks in the tubing and that tubing does not run under the patient. (Figure 6)
 - Secure tubing per hospital protocol.
- Step 11** Set vacuum to low, continuous suction at a minimum of 60mmHG. Always use the minimum amount of suction necessary.
- Step 12** Return patient's legs to a closed position.
 - Assess device periodically to ensure proper placement, particularly after turning or repositioning patient.
 - Device can be left in place for up to 24 hours. Replace device if soiled with stool or bodily fluids other than urine. Discard device according to hospital protocol and local regulations.

Removal

- Step 1** Place the patient in the supine position and separate patient's legs.
- Step 2** Gently remove the adhesive pad from the patient's abdomen.
- Step 3** Remove the patient's penis from the chamber.
- Step 4** Gently remove the base adhesive by pulling the tabs down and away from the patient's penis.
- Step 5** Assess skin integrity and perform perineal care.
- Step 6** Disconnect device from suction tubing and discard device according to hospital protocol and local regulations.

Discontinue use

- When independent or assisted toileting is feasible.
- During patient ambulation.

Product part identification:

[figure not shown]

Figure 1

[figure not shown]

Figure 2

[figure not shown]

Figure 3

[figure not shown]

Figure 4

[figure not shown]

Figure 5

[figure not shown]
[figure not shown]

Figure 6

Manufactured for: Sage Products LLC
 [name] • [name]
 [name] • stryker.com
 Assembled in U.S.A.
 U.S. Patents: stryker.com/patents

For a French-Canadian translated version of the instructions for use contact Stryker Customer Service at [name]. In Canada, this product is not intended to be sold to the general public.

R48050

6 18029 60044 8

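### The study's post-removal skin check names only the perineal area, so skin events under PrimoFit's abdominal adhesive pad rest on general instructions and may be under-recorded

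*Protocol*

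**What the plan says.** **After removal.** Protocol 7.5 step 9: "After removal, the HCP will note any signs of irritation/injury in the perineal area". The synopsis and 4.1 repeat the sentence. Step 9a, which says which skin findings become adverse events, sits beneath it.

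**Where the adhesive goes.** The risk table in Protocol 2.3.1 describes the two devices differently:
- PureWick: "PureWick™ MEC is an external device placed around the base of the penis and adhered to the pelvic skin".
- PrimoFit: "Sage PrimoFit™ is an external urine management device for the male anatomy that adheres to the pelvic and abdominal skin".

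The PrimoFit IFU (Appendix 2) agrees. Placement step 9 tells the user to "adhere the adhesive pad onto the patient's abdomen", and removal step 2 is "Gently remove the adhesive pad from the patient's abdomen".

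**Before placement.** The visual assessment in 7.5 step 2 covers the "pubic and genital region to ensure that the participant is trimmed and assess the anatomy". Exclusion criterion 4 is wider: "Has any irritation, wound, open lesion, at the application site, on the genitalia, perineum, or sacrum". Section 7.2 requires eligibility criteria that need a physical examination, skin condition among them, to be confirmed before a device is placed.

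**Analysis.** SAP section 7 provides adverse event and serious adverse event listings only. Protocol section 3 has no safety objective or endpoint.

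**The concern.** Skin injury and skin irritation are the two risks that 2.3.1 names for both devices, and both devices are held on by adhesive. A check meant to detect these harms should follow the adhesive. Step 9 instead names one area, and the abdomen is not in it. Because only PrimoFit has an abdominal pad, the omission falls on one arm of a within-subject comparison.

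What is at stake is even ascertainment of skin events. If abdominal findings are recorded less completely, the listings will make the comparator look somewhat better than it is. There is little chance to recover the information: the study is a single visit, participants leave after the second void and the surveys, and 11.3 says that missing observation data cannot be obtained from another source.

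**Working it through.** The point involves no formula, so the check sets the texts side by side.

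**1. Adhesive sites against the named area**

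| Device | Adhesive site (2.3.1; Appendices 1 and 2) | Within the area named in 7.5 step 9? |
|---|---|---|
| PureWick | Pelvic skin around the base of the penis | Yes, if perineal is read broadly |
| PrimoFit, base | Skin around the penis | Yes, if perineal is read broadly |
| PrimoFit, pad | Abdomen | No, on any reading |

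The broad reading is fair. Section 7.1 and the PureWick IFU use peri and perineal terms loosely for the genital and pubic region being prepared. Exclusion 4 does list the application site and the perineum separately, which points the other way, but the point does not need that to be settled: the abdomen lies outside either reading.

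**2. Other provisions that could reach the abdominal site**

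- *IFU at removal.* Step 8 of 7.5 requires removal according to the IFU. PrimoFit removal step 5 asks for a skin assessment without limiting the area, after both adhesives are off. It reaches the abdomen but carries no study recording instruction. The PureWick removal step in Appendix 1 has no counterpart.
- *Skin check during wear.* Section 4.1 calls for one at least every two hours, with no area stated. It applies while the device is on and the pad covers the skin. Monitoring lasts up to about 2 hours through one void, so removal may come first.
- *Adverse event definition (9.1.1).* It covers any body site, but only for what someone notices or reports. The comfort survey in Appendix 3 asks for comfort and recommendation ratings, not skin signs.
- *Before placement.* Section 7.2 with exclusion 4 reasonably covers the abdominal pad site as part of the application site. Step 2 of 7.5 does not mention it.

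**3. Extent**

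Each participant is planned to receive PrimoFit once, with one abdominal pad. The plan enrols about 50 participants to obtain 44 evaluable.

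- Lower figure: 44 × 1 = 44 applications.
- Upper figure: 50 × 1 = 50 applications.
- Adhesive sites per PrimoFit application: 2 (base and pad), of which 1 is outside the area named in step 9.
- PureWick adhesive sites on the abdomen: 0.

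The expected number of unrecorded events would need an irritation rate and a detection probability. The documents give neither.

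**4. Effect on the design figures**

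The stated 90% power at n = 44 for a difference of half a standard deviation reproduces: with a two-sided 0.05 paired t-test, the exact noncentral t gives 0.9000. The point uses none of these inputs, and widening the skin check would leave them unchanged.

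**The case against.** The strongest reply is that the abdomen is already covered. Step 8 makes the PrimoFit IFU part of the procedure, and that IFU requires a skin assessment after the pad has been peeled off. The professional doing the peeling is looking at the site and would see redness or injury, which is an adverse event wherever it occurs. Before placement, 7.2 and exclusion 4 apply to the application site. On the IFUs alone, PrimoFit gets more post-removal examination than PureWick, not less. Nor is any comparative safety analysis planned, and any under-recording would work against the sponsor's own device.

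Much of this stands, and it rules out several stronger readings that a reader might infer:
- *That abdominal injury is missed.* This does not follow. The IFU step and the general adverse event definition can both capture it.
- *That no examination covers the abdomen before or after PrimoFit.* The IFU removal step, and 7.2 with exclusion 4, contradict this.
- *That neither device's adhesive site is examined.* This needs a narrow anatomical reading of perineal that the documents' own loose usage does not support.
- *That the study fails to support a device comparison of skin events.* No such comparison is planned.

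What the reply does not remove is the mismatch in the study's own instruction. Step 9 is where the protocol tells the professional what to note after removal, and step 9a is where it says what must be recorded as an adverse event. The IFU assessment comes with no such instruction and exists for one device only, so the two devices are checked under different rules.

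**Conclusion.** The point holds in a limited form. The study-specific post-removal check omits PrimoFit's abdominal adhesive site, and abdominal adhesive events, possible only with PrimoFit, may therefore be under-recorded in the listings for that device. It applies to about 44 to 50 PrimoFit applications and one of the device's two adhesive sites. Any bias would favour the comparator; its size cannot be estimated from the documents.

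This rests on two assumptions: that staff follow step 9 as worded when deciding what to note, and that the case report form, which is not among the documents, does not already prompt for the abdominal site. If either fails, the gap is smaller. The primary, secondary, comfort and ease-of-use results are unaffected. The change is worth making because it concerns the main named safety risk and costs almost nothing.

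**What to change.** Reconcile the synopsis, 4.1 and 7.5 step 9 with the risk table in 2.3.1 and the PrimoFit IFU:

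- Have the professional note irritation or injury at every skin site the device adhered to (pelvic or pubic skin and, for PrimoFit, the abdominal pad site) as well as the genital and perineal area. Use one instruction for both devices.
- Make the skin check before placement cover the same sites, so that a later finding can be told from a pre-existing one.
- Record the body site of any finding, if the case report form does not already do so.

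The cost is a protocol wording change and perhaps a few form fields. The participant is already undressed and the professional is already removing the pad, so no visit, staff or sample size change is needed. The one small downside is that a few more mild skin events may be recorded.
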